## Weekly Responder Rate (Weeks 1, 2, 3, and 4)

Weekly responder rate will be assessed at each week and will be derived from the data on SBMs collected in the subject diary. Responder analysis will be performed at each week. A non-

CROSS-REGIONAL TEMPLATE			
Template Number:	C-TMPL-DO-801	Page:	25 of 31
Version Number:	1.2	Effective Date:	14 Sep 2015
This version replaces:	1.1		
Parent Document:	C-SOP-DO-800		
Template Title: S	tatistical Analysis Plan (Legacy Takeda)		

responder will be defined as any subject with a spontaneous BM frequency rate of less than 3 for a given week, any subject who dropped out during or prior to the given week due to lack of efficacy, or any subject who used rescue medication during or within 24 hours prior to the given week. Otherwise, the subject will be considered a responder. A responder with a spontaneous BM frequency rate  $\geq$  3 but <4 will be

considered a moderate responder. Otherwise, the subject will be a full responder ( $\geq$  4 SBM).

Weekly responder rate (non-responder/ moderate responder/ full responder) will be analyzed by van Elteren tests, stratified by center, at Weeks 1, 2, 3, and 4 separately. Additionally a cumulative logistic regression model will be used with treatment and center as factors as a sensitivity analysis. The estimated odds ratio and associated 95% CI will also be presented to aid interpretation of the clinical effect. The interaction between treatment and center will also be examined in a separate model.

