## 13.1.3 Efficacy Analysis

Two-sided tests at a significance level of  $\alpha$ =5% will be used throughout unless otherwise stated. The null hypothesis is that lubiprostone is equal to placebo against the alternative that lubiprostone is different to placebo. All analyses will be performed using the FAS. Analyses specified for the PP are to be regarded as supportive evidence. There will be no adjustment for multiplicity.

All efficacy endpoints will be summarized by treatment and visit. If baseline measures are also defined and collected for an efficacy endpoint then change from Baseline at each visit will also be presented by summary statistics by treatment and visit. Baseline is defined as the last recorded measurement prior to treatment. For parameters based on diary data, baseline values will be derived using the data from the Screening Period.

Centers may be pooled geographically if necessary for analysis purposes.

The LOCF technique will be used to impute missing values. For a given subject, the most recent nonmissing treatment-period data point will be carried forward to the subsequent week where data are missing. Supportive analyses will be conducted without missing value imputation (ie, without LOCF) and with a 'worse-case' scenario where missing values are assigned the worst case values recorded in the study by any subject for that endpoint at that time.

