As the primary endpoint is within the first week of study treatment and only 4 days of diary collection are required it is not anticipated that missing values should be a cause of concern therefore the LOCF technique will be used to impute missing values for efficacy analysis purposes only. For a given subject, the most recent nonmissing data point will be carried forward to the subsequent week where data are missing. Details for each efficacy parameter are given below. It is expected, based on previous studies, that the number of subjects with in-sufficient post baseline data for the primary endpoint will be small therefore a simple approach to handling missing data will be used. Where there is no post baseline efficacy data then the baseline value will be used, it is expected that the number of SBMs should increase for those on treatment, therefore using a baseline value for missing post baseline data assumes no treatment effect, this approach can be considered conservative,. To examine the effect of the requirement to have at least a minimum of 4 days post baseline efficacy data for the primary endpoint, using the stratified van Elteren test [2], will be conducted using all valid SBM data post baseline even when less than 4 days data is present, only where there is no post baseline data will baseline be used in this analysis.

An SBM is defined as any BM that does not occur within 24 hours after rescue medication use. Certain periods after taking rescue medication will be defined as "blackout periods" during which BMs are considered as non-spontaneous. Blackout periods, including those with missing or partial times for rescue medication use in the diary, will be handled as follows:

0-24 hours post rescue medication intake if the time is fully specified.

0-24 hours post rescue medication intake if the hour is present, but the minute is missing. The blackout time will commence from the imputed time. If the minutes are incomplete or missing from either the rescue medication or bowel movement entry then it is assumed that the missing values are zero and an imputed time will be calculated. e.g.

1	5	_	_	=	1	5	0	0
2	1	5		=	2	1	5	0

0-48 hours, beginning from midnight on the day the rescue medication intake is recorded for, if the hour is missing from the time entry for the rescue medication.

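### Under LOCF, a subject who leaves for a reason other than lack of efficacy with a last weekly SBM rate of at least 3 counts as a weekly responder after leaving the study

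*SAP*

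**What the plan says.** **Definition.** SAP 7.8.2, Weekly Responder Rate, makes a subject a non-responder for a given week in three cases: the weekly SBM rate is below 3; the subject is "any subject who dropped out during or prior to the given week due to lack of efficacy"; or rescue medication was used in the week or in the 24 hours before it. For the rest: "Otherwise, the subject will be considered a responder". A rate from 3 to below 4 is a moderate response and 4 or more a full response. Protocol 9.1.7.6 and 13.1.3.2 give the same rule. The status is "derived from the data on SBMs collected in the subject diary".

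**Missing data.** Protocol 13.1.3 states for efficacy in general: "The LOCF technique will be used to impute missing values". It adds supportive analyses without LOCF and with a worst case in which "missing values are assigned the worst case values recorded in the study by any subject for that endpoint at that time". SAP 7.8 says that "the most recent nonmissing data point will be carried forward to the subsequent week where data are missing", and promises: "Details for each efficacy parameter are given below". It also says: "Where there is no post baseline efficacy data then the baseline value will be used".

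**Endpoint detail.** SAP 7.8.2 then sets out the handling of missing data for SBM frequency (Week 2 only), SBM within 24 hours, straining, stool consistency and abdominal symptoms, and SAP 7.8.3 does so for PAC-QOL. The responder section has no such text.

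**Dropout reasons.** SAP 7.3 and Protocol 7.5 list adverse event, loss to follow-up and voluntary withdrawal as categories separate from lack of efficacy.

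**The concern.** Protocol 6.2 gives weekly responder rates, together with SBM frequency at other time points, the task of supporting a continuous effect. A subject who responds in Week 1, stops for an adverse event and is scored a responder at Weeks 2, 3 and 4 is not evidence of that. By then the subject is off treatment, and diary-keeping does not extend into follow-up (Protocol 9.3.5; Appendix A, footnote j). The rule treats stopping for lack of efficacy as failure but lets an earlier value stand for stopping because of intolerance or unexplained loss. If such dropout differs between arms, the responder difference at later weeks moves with it. The supportive analyses that would reveal this are promised in the protocol but are not specified for this endpoint in the SAP.

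**Working it through.** The plan gives no figure for this endpoint, so there is none to reproduce. The check applies the rule to cases and then sizes the effect under stated assumptions.

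**1. The rule applied.** Take a subject who stops at the end of Week 1 with no rescue use.

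| Reason for stopping | Week 1 rate | Status at Weeks 2 to 4 under LOCF |
|---|---|---|
| Adverse event | 6 | full responder |
| Adverse event | 3.5 | moderate responder |
| Adverse event | 2 | non-responder |
| Lack of efficacy | 6 | non-responder |

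An adverse-event dropout on Day 2 has no Week 1 rate, because fewer than 4 days are available. SAP 7.8 then uses baseline. Eligibility requires fewer than 3 SBMs per week (Protocol 7.1 and 7.2), so this subject is a non-responder. The problem is confined to subjects whose last post-baseline rate is at least 3.

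**2. The planned dropout figure does not help.** The 3% by Day 4 in Protocol 13.3 and SAP 6.0 concerns subjects with too few days for a Week 1 rate. They take the baseline value and are non-responders. Neither document gives dropout to Week 4, by arm or by reason.

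**3. Size formula.** Let d be the proportion of an arm that drops out for reasons other than lack of efficacy, and r the proportion of those dropouts whose last rate is at least 3. LOCF adds d × r to that arm's responder rate, compared with counting them as non-responders. The treatment difference shifts by dL × rL − dP × rP (L = lubiprostone, P = placebo). One subject is 1/75 = 1.3 points.

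**4. Values for r (assumption).** Set r equal to the arm's Week 1 probability of 3 or more SBMs, from a negative binomial matched to each mean m and SD s in Protocol Table 4.a, with size k = m²/(s² − m). For SC0131 on lubiprostone, k = 5.69²/(4.41² − 5.69) = 2.35, which gives 0.743. SE = √[rL(1 − rL)/75 + rP(1 − rP)/75].

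| Study | rL | rP | SE (points) |
|---|---|---|---|
| SC0131 | 0.743 | 0.616 | 7.6 |
| SC0232 | 0.797 | 0.669 | 7.1 |
| SC0831 | 0.857 | 0.548 | 7.0 |

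**5. Shift in the responder difference, in points (dropout rates assumed).**

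| Dropout, L vs P | SC0131 | SC0232 | SC0831 |
|---|---|---|---|
| 2% vs 2% | +0.3 | +0.3 | +0.6 |
| 8% vs 8% | +1.0 | +1.0 | +2.5 |
| 8% vs 2% | +4.7 | +5.0 | +5.8 |
| 2% vs 8% | −3.4 | −3.8 | −2.7 |

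Example, SC0131 at 8% vs 2%: 8 × 0.743 − 2 × 0.616 = 4.7. The 8% vs 2% shifts are about 0.6 to 0.8 standard errors. The sign changes when dP/dL = rL/rP, that is 1.2 for the US studies and 1.6 for the Japanese study. If dropouts respond at half their arm's rate, every figure halves.

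**6. Dependence on the model.** A continuous gamma fit to SC0131 gives about 68% and 50%. Equal 8% dropout then gives 8 × 0.187 = 1.5 points instead of 1.0.

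**The case against.** **LOCF is already general, and the SAP points to carrying the rate.** This largely stands. SAP 7.8 sets LOCF for efficacy, the SBM frequency text carries the weekly estimate, and responder status is derived from SBM data. The natural reading is to carry the rate and then apply the thresholds. What is missing is a sentence saying so, and that alone would be minor.

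**The definition looks deliberate and supports comparison.** The wording is the same in three places, Table 4.a reports the US studies under LOCF, and Protocol 6.2 calls this a bridging study. Whether an adverse-event dropout is a failure is a choice of estimand, and the documents do not contradict themselves on it. This stands as a reason to keep LOCF as a sensitivity analysis. It does not answer the mismatch with the purpose that Protocol 6.2 gives the endpoint.

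**The worst-case analysis already covers it.** In part. Protocol 13.1.3 plans it in general terms. The SAP details the worst case only for SBM frequency (7.8.1 and 7.8.2) and does not mention an analysis without LOCF.

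**LOCF affects the other weekly endpoints too.** True. The mismatch is sharpest here, because this definition already treats one kind of dropout as failure.

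**Stronger readings that the documents do not support.** A reader might infer that a subject with a missing rate falls through the closing clause and becomes a full responder. SAP 7.8 fills missing rates by LOCF, or by baseline, and a full response is tied to 4 or more SBMs. A reader might also infer that the rule favours lubiprostone. That needs dropout by arm, which is not given, and the shift can take either sign.

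**Conclusion.** The point holds as a weakness in a secondary analysis. Following the stated rules, a subject who stops for a reason other than lack of efficacy, with a last rate of at least 3 and no rescue use, is scored a responder in weeks off study. That does not fit the purpose the protocol gives the endpoint. The wording gap is smaller: the carried rate is implied but not stated, and the protocol's supportive analyses are not brought over to this endpoint.

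The effect is small if dropout is low and balanced. It becomes material only if dropout differs clearly between arms; 8% vs 2% is an illustration with no source in the documents. The figures use Week 1 response in the earlier studies for dropouts' last week, ignore rescue use and treat response as binary. The effect on the planned van Elteren test over three ordered categories was not computed. Confidence is medium. The primary analysis and sample size are not affected.

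**What to change.** Add to SAP 7.8.2, Weekly Responder Rate, with an entry in SAP 7.13:

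1. A subject who has discontinued for any reason and has fewer than 4 evaluable diary days in the week is a non-responder for that week.
2. Lack-of-efficacy dropout and rescue use remain non-response as now defined.
3. For a subject still on treatment with fewer than 4 diary days in the week, the most recent weekly SBM rate is carried forward and the status derived from it. If there is no earlier post-baseline rate, the baseline value is used as in SAP 7.8, which gives non-response for an eligible subject.
4. The full-LOCF analysis is reported as a sensitivity analysis for comparison with the earlier studies. The no-LOCF and worst-case analyses of Protocol 13.1.3 apply to this endpoint, with non-responder as the worst value.

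The cost is four items of SAP text, one entry in the changes section and one extra set of tables. Responder rates will be slightly lower, and the main analysis of this endpoint departs from full LOCF; item 4 preserves the comparison. Protocol 13.1 has the SAP finalised before unblinding, so the change should be made by then.

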7.8.3 Additional Efficacy Endpoint(s)

PAC-QOL Questionnaire:

The PAC-QOL will be analyzed separately for the first 24 items that comprise the Dissatisfaction Index and for the last 4 items that comprise the Satisfaction Subscale at Baseline, and at Weeks 2 and 4. As the PAC-QoL is performed during the visit missing data should only occur when the entire questionnaire is missing, rather than individual items. When the PAC-QoL is missing then LOCF will be used to carry forward the nearest previous value.

The Dissatisfaction Index will be analyzed using van Elteren's test stratified by center to examine the difference between lubiprostone and placebo. Additionally the endpoint will be analyzed using ANOVA models with center and treatment in the model as a sensitivity analysis. The estimated LS means, related mean difference and associated 95% CI will also be presented to aid interpretation of the clinical effect.

The Satisfaction Index will be categorized by combined scores of the 4 items as either poor (0-4), fairly good (5-8), good (9-12), or excellent (13-16) and will be analyzed by van Elteren tests, stratified by center, at Baseline, and at Weeks 2 and 4 separately. Additionally a cumulative logistic regression model will be used with treatment and center as factors as a sensitivity analysis. The estimated odds ratio and associated 95% CIs will also be presented to aid interpretation of the clinical effect.

CROSS-REGIONAL TEMPLATE			
Template Number:	C-TMPL-DO-801	Page:	26 of 31
Version Number:	1.2	Effective Date:	14 Sep 2015
This version replaces	s: 1.1		
Parent Document:	C-SOP-DO-800		
Template Title:	Statistical Analysis Plan (Legacy Takeda)		

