### 9.1.8 Additional Endpoints

## 9.1.8.1 Quality of Life Evaluation

The PAC-QOL is a health related QOL instrument designed specifically to evaluate an adult subject's assessment of constipation over time. It is self administered assessment consisting of 28 items and is designed to cover the 2 weeks prior to the questionnaire being completed. Each item is scored from 0 to 4; a lower score is better. The 28 items are grouped into 4 subscales: physical discomfort, psychosocial discomfort, worries and concerns, and satisfaction.

The PAC-QOL will be assessed at Day -1 (prior to the start of study drug), mid-way through the Double-Blind Treatment Period on Day 15, and at the end of the Double-Blind Treatment Period, on Day 29.

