### 13.1.3.3 Additional Endpoints

#### **Efficacy**

PAC-QOL Questionnaire: The PAC-QOL will be analyzed separately for the first 24 items that comprise the Dissatisfaction Index and for the last 4 items that comprise the Satisfaction Subscale at Baseline, and at Weeks 2 and 4.

The Dissatisfaction Index will be analyzed using van Elteren's test stratified by center to examine the difference between lubiprostone and placebo. Additionally the endpoint will be analyzed using ANOVA models with center and treatment in the model as a sensitivity analysis. The estimated LS means, related mean difference and associated 95% CI will also be presented to aid interpretation of the clinical effect.

The Satisfaction Index will be categorized by combined scores of the 4 items as either poor (0-4), fairly good (5-8), good (9-12), or excellent (13-16) and will be analyzed by van Elteren tests, stratified by center, at Baseline, and at Weeks 2 and 4 separately. Additionally a cumulative logistic regression model will be used with treatment and center as factors as a sensitivity analysis. The estimated odds ratio and associated 95% CIs will also be presented to aid interpretation of the clinical effect.

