#### **Additional Endpoints**

Quality of life evaluation using the standard Patient Assessment of Constipation-Quality of

Life (PAC-QOL) Questionnaire.

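### The PAC-QOL Satisfaction sum (0-16) is cut into four bands before a rank test that could use the sum itself, it is also tested at Baseline, and its scoring direction is not reconciled

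*SAP*

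**What the plan says.** SAP 7.8.3 splits the PAC-QOL into a Dissatisfaction Index (first 24 items) and a Satisfaction part (last 4 items). The two parts are treated differently.

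- **Dissatisfaction Index.** The score goes straight into the rank test: "The Dissatisfaction Index will be analyzed using van Elteren's test stratified by center to examine the difference between lubiprostone and placebo".
- **Satisfaction Index.** The sum "will be categorized by combined scores of the 4 items as either poor (0-4), fairly good (5-8), good (9-12), or excellent (13-16". These bands "will be analyzed by van Elteren tests, stratified by center, at Baseline, and at Weeks 2 and 4 separately". A cumulative logistic regression with treatment and center is the sensitivity analysis, reported as an odds ratio.

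Protocol 13.1.3.3 (Additional Endpoints, Efficacy) has the same bands, test and time points: "The Satisfaction Index will be categorized by combined scores of the 4 items as either poor (0-4), fairly good (5-8), good (9-12), or excellent". Neither document gives a reason for banding one part and not the other.

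On item scoring, Protocol 9.1.8.1 says: "Each item is scored from 0 to 4; a lower score is better". It makes no exception for the four satisfaction items.

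PAC-QOL is listed under additional endpoints, below primary and secondary, and there is no multiplicity adjustment.

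**The concern.** Three things in this one analysis deserve attention.

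1. **Banding before ranking.** Four items scored 0-4 give a sum with 17 possible values. The van Elteren test handles such a score through mid-ranks. Cutting it into four bands makes every pair of subjects within a band a tie: a sum of 5 and a sum of 8 are equal, while 4 and 5 differ. That discards ordering information which the test could use.
2. **A between-group test at Baseline.** PAC-QOL baseline is taken on Day -1, before study drug. In a randomised trial a difference there can only arise by chance, so the p-value answers no question about treatment. Protocol 13.1.2 already has baseline characteristics summarised descriptively.
3. **Direction.** If a lower score is better, a sum of 0-4 should be the most favourable band, yet it is labelled *poor*, and 13-16 is labelled *excellent*. Without a reverse-scoring rule, a reader cannot tell which way the odds ratio points.

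At stake are some power and a clear reading of one quality-of-life result. The primary and secondary conclusions are not affected.

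**Working it through.** **Number per arm.** The plan states no power or sample size for this score, so the number per arm comes from the primary endpoint (SAP 6.0). The average-variance SD is sqrt((2.7² + 4²)/2) = sqrt(11.645) = 3.41, and the difference is 5.9 - 4 = 1.9. A t-test at 90% power and two-sided 0.05 needs 69 per arm. Multiplying by π/3 for the Wilcoxon test gives 72.3, rounded up to 73 per arm, or 146 in total, which is the plan's figure. The checks below use 73 (evaluable) or 75 (randomised) per arm.

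**Formula.** Let θ = P(Y > X) + ½P(Y = X) - ½, and let p_k be the average proportion in category k. The noncentrality of the mid-rank Wilcoxon test is (n/2) × 12θ² / (1 - Σp_k³), with n per arm. Relative efficiency is this quantity for the four bands divided by the same quantity for the 17 levels. Information loss is 1 minus relative efficiency.

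**A best-case benchmark by hand.** Under a small proportional-odds shift, efficiency is approximately proportional to 1 - Σp_k³. Four equally filled bands give 1 - 4 × (1/4)³ = 0.9375, so even well-placed bands lose about 6%.

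**Check 1: clipped normal (assumed).** Scores are normal, rounded and clipped to 0-16, with a shift of 0.45 SD and 75 per arm.

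| Centre | SD | Relative efficiency | Loss | Power, sum | Power, bands |
|---|---|---|---|---|---|
| 8 | 5 | 0.918 | 8.2% | 75.1% | 71.5% |
| 8 | 3 | 0.885 | 11.5% | 75.1% | 69.9% |
| 6 | 3 | 0.862 | 13.8% | 75.1% | 68.7% |
| 5 | 2.5 | 0.797 | 20.3% | 74.9% | 65.2% |
| 4 | 3 | 0.753 | 24.7% | 74.7% | 62.5% |
| 3 | 2 | 0.564 | 43.6% | 74.4% | 50.2% |

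With centres from 5 to 10 and SD 2.5 to 5, the loss is 8.2-20.3%. With SD 2 at those centres it is about 22-24%, with the centre at 12 it is 13-24%, and with the centre at 3-4 it is 18-44%.

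**Check 2: beta-binomial sums (assumed).** The placebo mean is 25-50% of the maximum, the shift 11-12% of the range, with 73 per arm and three dispersions. Relative efficiency is 0.77-0.92, so the loss is 8-23%, and power falls by about 3 to 11 points. Simulated examples, sum versus bands: 80.4% versus 77.1% (placebo mean 45% of maximum), 81.7% versus 77.6% (35%), and 85.6% versus 77.1% (25%).

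**Check 3: stratification.** A simulated van Elteren test with 10 centers of 15 subjects (1,500 runs per setting, five mid-scale settings) gave relative efficiency from 0.948 down to 0.798, a loss of about 5-20%.

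No setting favoured the bands.

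**Direction.** The bands hold 5, 4, 4 and 4 values. As written, the cuts fall at 4/5, 8/9 and 12/13. If the score is reversed (16 minus the sum), the same labels cut the original sum at 3/4, 7/8 and 11/12. Take two subjects with sums 4 and 5. As written they fall in different bands; reversed, they become 12 and 11 and tie. For sums 3 and 4 it is the other way round: tied as written, separated (13 and 12) when reversed. The banded p-value therefore depends on a coding choice that the plan does not state. A two-sided rank test on the sum gives the same p-value under either coding.

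**The case against.** The best defence is that banding is a deliberate, prespecified and consistent choice. The bands supply named categories and a four-level cumulative odds ratio that the SAP presents to help clinical reading. Weekly responder rate is handled the same way: a frequency cut into ordered classes, then van Elteren plus cumulative logistic regression. This stands as a reason to keep the bands for description and for the logistic model, so it would be wrong to infer that the bands serve no purpose. It is not a reason to feed them to the rank test. Unequal width is also not an error in itself, since 17 values cannot be split into four equal bands.

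The second defence is that the loss cannot be derived from the documents, which give no mean, SD or expected effect for this score. That is correct. A reader might take one percentage as a property of the plan; it is only a range under assumptions. The direction of the loss is stable, its size is not.

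Third, little hangs on it. The endpoint is additional, no power was claimed for it, and the error is toward missing an effect, not toward a false positive. The Baseline p-value is uninformative, but nothing in either document uses it to choose a model, covariate or analysis set. All of this stands and keeps the point minor.

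**Conclusion.** The point holds as a low-weight improvement. Banding before the van Elteren test costs roughly 8-23% of the information, about 3 to 11 power points, under assumed and mostly mid-scale distributions with 73 to 75 per arm and power of roughly 75-86% on the sum. A simulation with center strata gave about 5-20%, and scores clustered near the low end could lose up to about 44%. The Baseline test should go because its result has no treatment interpretation.

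The conflict in scoring direction matters most for interpretation. A reader might infer that the benefit will be reported backwards. The documents do not show that: they do not say how the four satisfaction items are coded in the database, and a reversal may be intended but unwritten. What they do show is that Protocol 9.1.8.1 and the band labels cannot both apply without a rule that is missing.

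**What to change.** In SAP 7.8.3:

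1. Run the van Elteren test on the 0-16 Satisfaction sum at Weeks 2 and 4.
2. Keep the four bands for the descriptive table and for the cumulative logistic model.
3. Summarise Baseline by treatment group without a test. The section's opening sentence lists Baseline for both PAC-QOL parts, so make this clear for the Dissatisfaction Index too.
4. Reconcile Protocol 9.1.8.1 with the band labels: state how the four items are coded, whether they are reversed, and which direction of the sum and of the odds ratio favours lubiprostone.
5. Record the departure from Protocol 13.1.3.3 in SAP 7.13, or in an amendment, before unblinding. SAP 7.13 now mentions only added detail and additional analyses, so changing 7.8.3 alone would leave an unexplained discrepancy.

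No new data are needed, because the sum is already computed to form the bands. The cost is a documented change between protocol and SAP, and a main p-value for this endpoint that no longer refers to the labelled bands.
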